6.2.1 Screening and run-in period(s)

Visit 1 will be conducted on the same day as EOT_B of the parent trial, INBUILD[®] so that there is no interruption of treatment. The trial will be explained to all patients who completed INBUILD[®] (who didn't discontinue treatment) and are willing to continue or start treatment with nintedanib. This may be done prior to Visit 1, however no trial related procedure or data collection should be performed until the patient has signed the Informed Consent for the extension trial at Visit 1.

Upon obtaining informed consent, the investigator will register the patient in the IRT system and the patient will receive a trial identification card.

Assessments conducted as part of EOT_B of the INBUILD[®] trial do not need to be repeated for Visit 1 of this extension trial.

If the patient has been determined eligible by the investigator to enter the trial (refer to section [3.3](#)), medication will be assigned to the patient via the IRT system (refer to section [4.1.3](#)). First dose of nintedanib within INBUILD[®]-ON will be administered in the clinic at Visit 1. Data from the EOT_B assessments will be transferred to INBUILD[®]-ON as baseline data. All AEs ongoing at the EOT_B visit of INBUILD[®] will be recorded as baseline conditions in INBUILD[®]-ON.

6.2.2 Treatment period(s)

Subsequent clinic visits will be scheduled after 2, 4, 8, 12, 24, 36 and 48 weeks of treatment (Visits 2- 8). After the first 48 weeks of treatment (Visit 8), complete clinic visits will be scheduled every 12 weeks until at least Week 96 (Visit 12) and thereafter until the patient's end of trial.

Intermediate lab tests ('a' visits) will be performed if needed at 18, 30 and 42 weeks (Visits 5a, 6a and 7a) at the discretion of the investigator. The laboratory samples taken at these visits and any samples taken for additional safety monitoring (see sections [4.2.1.2](#) and [5.2.3](#)) may be collected at the office of a local doctor using trial specific lab kits that will be sent to a central laboratory for analyses. These kits will be provided to patients at study visits as applicable.

If possible, ECG should be performed prior to blood draw.

For detailed description of the trial procedures at each visit and dispensing schedule, please refer to [section 5](#) and the [Flowchart](#).

Dose Modification Visit

If the dose is reduced or increased (refer to section [4.1.3](#)) patients may need to come to the investigational site for a dose modification visit where the following will be performed:

- Physical examination including weight
- Vital signs

- Assessment of adverse events and concomitant therapy since last visit
- Assignment of new dose in IRT and trial medication dispensation
- Trial medication will be collected and drug accountability and treatment compliance will be reviewed

End of Treatment (EOT)

If a reason for drug discontinuation is met or when the trial is terminated due to one of the reasons mentioned in section [3.3.4](#), an End of Treatment Visit (EOT) should be scheduled as soon as possible after last drug intake for all patients. Reason for discontinuation must be documented in the eCRF. IRT should always be notified on end of treatment (EOT).

Adverse events that are ongoing at EOT should be followed up according to section [5.2.5.2.3](#).

For detailed description of the trial procedures at the EOT visit, please refer to the [Flowchart](#).

6.2.3 Follow up period and trial completion

A follow-up (FU) visit must be conducted 28 days after last drug intake if trial medication was discontinued permanently due to adverse events. A FU visit does not need to be conducted for patients who stop for any other reason.

For detailed description of the trial procedures at the FU visit, please refer to the Flowchart.

If the reason for removal of a patient from the treatment is an adverse event, the patient must be followed until complete resolution or stabilization of the event for at least 28 days after the onset of the event or until follow-up is considered adequate by the investigator and clinical monitor.

A patient will be lost to follow-up if the investigator is not able to contact him/her despite multiple attempts. Every effort must be made; at least 2 telephone contacts plus 1 mailing should be documented. The site must notify the clinical monitor prior to designating a patient as lost to follow up.

For patients who permanently discontinue nintedanib due to adverse events, the FU Visit will be the trial completion visit. For all other patients the EOT visit will be the trial completion visit.

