7.3.4 Safety analyses

Adverse events will be coded using the Medical Dictionary for Drug Regulatory Activities (MedDRA). Standard BI summary tables and listings will be produced. All adverse events with an onset between start of treatment and end of the REP, a period of 28 days after the last dose of trial medication, will be assigned to the on-treatment period for evaluation.

All treated patients will be included in the safety analysis. In general, safety analyses will be descriptive in nature and will be based on BI standards. No hypothesis testing is planned.

Statistical analysis and reporting of adverse events will concentrate on treatment-emergent adverse events, i.e. all adverse events occurring between start of treatment and end of the REP. Adverse events that start before first drug intake and deteriorate under treatment will also be considered as 'treatment-emergent'.

Frequency, severity, and causal relationship of adverse events will be tabulated by system organ class and preferred term after coding according to the current version of the Medical Dictionary for Drug Regulatory Activities (MedDRA) at database lock.

Laboratory data will be analysed both quantitatively as well as qualitatively. The latter will be done via comparison of laboratory data to their reference ranges. Values outside the reference range as well as values defined as clinically relevant will be summarised. Treatment groups will be compared descriptively with regard to distribution parameters as well as with regard to frequency and percentage of patients with abnormal values or clinically relevant abnormal values.

Vital signs, physical examinations, or other safety-relevant data observed at screening, baseline, during the course of the trial and at the end-of-trial evaluation will be assessed with regard to possible changes compared to findings before start of treatment.

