6. GENERAL ANALYSIS DEFINITIONS

6.1 TREATMENTS

For treatment specifications, please refer to CTP Section 4.

The different periods of interest, as per CTP flow chart, are the following:

Note: the last day of each of the periods is excluded from the period. It defines the first day of the subsequent period.

- Post-IC period (optional^[a]): From date of informed consent to first nintedanib intake.
- Treatment period: From first nintedanib intake (or re-start of treatment if interruption) to last nintedanib intake (or day before start date of interruption if interruption) plus one day.
- Off-treatment (optional^[a]): From start date of interruption to re-start of treatment.
- Residual effect period^[b]: From last nintedanib intake plus one day to last nintedanib intake plus 28 days plus one day.
- Follow-up period (optional^[a]): From last nintedanib intake plus 28 days plus one day (after residual effect period) to last contact date (as collected on the end of study eCRF page) plus one day. This period is only created if last nintedanib intake took place more than 28 days before last contact date (as collected on the end of study eCRF page).
- Post-study period (optional^[a]): From last nintedanib intake plus 28 days plus one day or from last contact date (as collected on the end of study eCRF page) plus one day, whichever occurs later.

^[a] This period is optional insofar as it does not necessarily exist for all subjects.

^[b] In addition, a residual effect period of 7 days will be used for safety analyses to more closely reflect the period of time after the last nintedanib intake.

For subjects who did not receive any dose of nintedanib in extension trial, Post-IC period is the only period defined.

For subjects who died during the trial, periods with above defined start date after date of death do not exist and last existing period is defined until date of death plus one day only.

For safety analyses ([Section 7.8](#)), data from the treatment period, possible off-treatment periods and residual effect period will be considered as on-treatment.

6.2 **IMPORTANT PROTOCOL DEVIATIONS**

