6.7 BASELINE, TIME WINDOWS AND CALCULATED VISITS

As a general rule, the last assessment/measurement before or on the date of Visit 1 will be used as baseline.

Visit windowing will be performed as described in [Tables 6.7: 1, 6.7: 2](#) and [6.7: 3](#), in order to assign data to the relevant study visit based on the actual day of the assessment. Data will be analysed using the re-calculated visits in the statistical tables. However, in the listings, all visits performed will be displayed (even if outside time-window), along with the re-calculated visit. No time-windowing will be performed for the follow-up visit, i.e. follow-up visit will be displayed in listings (where applicable) whenever it was performed. A follow-up visit is only scheduled for subjects who prematurely discontinued nintedanib due to adverse event.

Table 6.7: 2 Time windowing rules for physical exam and vital signs

Time window of actual day ^[1]			Allocated to		
Start day	End day (included)	Length of the time-window [days]	Visit number	Visit name	Planned day of the visit
1	1	1	1	Baseline	1
2	22	21	2	2 weeks	15
23	43	21	3	4 weeks	29
44	71	28	4	8 weeks	57
72	127	56	5	12 weeks	85
128	211	84	6	24 weeks	169
212	295	84	7	36 weeks	253
296	379	84	8	48 weeks	337
380	463	84	9	60 weeks	421
464	547	84	10	72 weeks	505
548	631	84	11	84 weeks	589
632	715	84	12 (p)	96 weeks	673 (V _p)
$\frac{V_p + 1}{2} + \frac{V_{p+1} - V_p}{2}$	$\frac{V_{p+1}}{2} + \frac{V_{p+2} - V_{p+1}}{2}$	$\frac{V_{p+2} - V_p}{2}$	p + 1	...	$V_{p+1} = V_p + 12 \times 7$
...	Every 12 weeks thereafter	...

V_p denotes the planned day of the visit

[1] Date of Visit 1 in extension trial is taken into account as a reference to calculate time windows

Table 6.7: 3 Time windowing rules for laboratory measurements (and pregnancy test)

Time window of actual day ^[1]			Allocated to		
Start day	End day (included)	Length of the time-window [days]	Visit number	Visit name	Planned day of the visit
1	1	1	1	Baseline	1
2	22	21	2	2 weeks	15
23	43	21	3	4 weeks	29
44	71	28	4	8 weeks	57
72	106	35	5	12 weeks	85
107	148	42	5a ^[2]	18 weeks	127
149	190	42	6	24 weeks	169
191	232	42	6a ^[2]	30 weeks	211
233	274	42	7	36 weeks	253
275	316	42	7a ^[2]	42 weeks	295
317	379	63	8	48 weeks	337
380	463	84	9	60 weeks	421
464	547	84	10	72 weeks	505
548	631	84	11	84 weeks	589
632	715	84	12 _(p)	96 weeks	673 (V_p)

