7.8 SAFETY ANALYSIS

All safety analyses will be performed over the whole trial on the treated set. Similar summaries will be provided regarding the first 48 weeks or the first 96 weeks only.

The analysis of safety data will be based on the concept of treatment emergent AEs or measurements. That means that, for analyses over the whole trial, all AEs/laboratory or vital sign measurements occurring between first nintedanib intake till last nintedanib intake + 28 days will be assigned to the on-treatment period. For analyses over 48 weeks and 96 weeks respectively the on-treatment period is defined from date of first nintedanib intake until date of last nintedanib intake + 28 days, or until Week 48/Week 96 time point (Day 379/ Day 715, i.e. 378/714 days after date of Visit 1), if earlier.

All analyses will be performed according to randomised treatment group in the parent trial and overall.

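### Crude SAE, severe-AE and fatal-AE percentages count 28 days after the last dose that are only partly observed when patients stop for reasons other than an AE: a small under-count, cheap to remedy

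*Protocol*

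**What the plan says.** **Counting window.** Protocol 7.3.4 assigns to the on-treatment period "All adverse events with an onset between start of treatment and end of the REP, a period of 28 days after the last dose". SAP 6.1 agrees: "data from the treatment period, possible off-treatment periods and residual effect period will be considered as on-treatment". SAP 7.8 applies the same limit to "all AEs/laboratory or vital sign measurements occurring between first nintedanib intake till last nintedanib intake + 28 days". For the 48- and 96-week analyses the window ends there "or until Week 48/Week 96 time point (Day 379/ Day 715, i.e. 378/714 days after date of Visit 1), if earlier". The rule is the same whatever the reason for stopping.

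**Collection window.** Protocol 5.2.5.2.1 has all AEs entered in the CRF until the individual patient's end of trial. Afterwards only cancers, related SAEs and related AESIs that come to the investigator's attention are reported, on the SAE form and not in the CRF. Under Protocol 6.2.3 the end of trial is the 28-day follow-up (FU) visit for patients who stop because of an AE, and the EOT visit for everyone else: "A FU visit does not need to be conducted for patients who stop for any other reason". SAP 6.7 confirms it: "A follow-up visit is only scheduled for subjects who prematurely discontinued nintedanib due to adverse event". Protocol 6.2.2 says that EOT "should be scheduled as soon as possible after last drug intake for all patients".

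**Analysis.** SAP 7.8.1 counts subjects with AEs, and SAP 7 takes percentages of the whole treatment group. Exposure-adjusted rates are planned for the whole-trial SOC/PT table and its version for terms above 5% (SAP 7.8.1), the safety-topic tables (7.8.1.2) and the primary endpoint (7.8.1.4). Time at risk ends at the earliest of last dose + 28 days, last contact, death or database lock (7.8.1.1). SAP 6.1 also says: "In addition, a residual effect period of 7 days will be used for safety analyses". No output in the visible text of SAP 7.8 is tied to that 7-day period.

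**The concern.** For a patient who stops for a reason other than an AE, the tables count a window in which new events are not collected after EOT. A new, unrelated, non-cancer SAE that starts on day 15 after the last dose is entered if the patient stopped for an AE. If the patient stopped for another reason and EOT has already taken place, it need not be reported at all. Ascertainment thus depends on the reason for stopping, and the error is always downward.

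The affected group exists by design: under Protocol 3.1, patients who can obtain nintedanib outside the trial have their EOT visit at Week 96. Long-term safety is the trial's main objective, so the SAE and fatal-AE percentages will be read as a safety profile. SAP 7.8.1 lists the SAE, severe-AE and fatal-AE tables separately, after the sentence on exposure-adjusted rates, and does not say that rates accompany them. SAP 7.8.1.1 plans rates for whole-trial analyses only, so the 48- and 96-week tables have none.

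**Working it through.** The plan gives no figure to reproduce here: the trial is descriptive, without a sample-size calculation or expected AE rates. The check compares the two windows and then sizes the gap.

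**1. Length of the gap.** Let L be the days from last dose to EOT. The plan says only that EOT comes as soon as possible, so L = 0 to 7 is assumed. The unobserved part is 28 − L = 21 to 28 days. As a share of the counted window at Week 96 (672 days on treatment):
- L = 0: 28/(672 + 28) = 4.0%
- L = 7: 21/700 = 3.0%

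The gap shrinks, and can vanish, when an interruption becomes permanent and EOT follows the last intake by weeks.

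**2. The 96-week table.** A last dose on Day 673 gives a window to 673 + 28 = Day 701, inside the Day 715 limit. The whole unobserved stretch is therefore counted in that table. In the 48-week table it arises only for patients whose last dose precedes the Day 379 limit.

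**3. Illustration with a documented incidence.** Protocol 1.2 gives bleeding AEs in 11.1% of the parent trial's nintedanib group over 52 weeks (364 days). Bleeding stands in here for any event of that frequency. With a constant hazard:
- h = −ln(1 − 0.111)/364 = 0.000323 per day
- missed = exp(−h(672 + L)) − exp(−h × 700)
- L = 0: 0.8048 − 0.7975 = 0.0073, or 0.73 points
- L = 7: 0.8029 − 0.7975 = 0.0054, or 0.54 points
- full count: 1 − 0.7975 = 20.2%, so the relative under-count is 3.6% (L = 0) or 2.7% (L = 7)

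Using the parent placebo incidence (12.7%) for the hazard after the last dose gives 0.84 and 0.63 points. The result does not depend on carrying an on-drug hazard into the off-drug period.

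**4. Total column.** Let f be the share of about 480 patients who stop for a non-AE reason. The documents do not give f; 10-80% is assumed. Points = f × missed; patients = 480 × f × missed.

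| f | L (days) | Points | Patients |
|---|---|---|---|
| 0.1 | 7 | 0.05 | 0.3 |
| 0.5 | 0 | 0.36 | 1.7 |
| 0.8 | 0 | 0.58 | 2.8 |

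**5. SAEs and fatal AEs.** Their rates are not in the documents. On purely assumed rates, with f = 60-90%, L = 0 and 96 weeks of treatment:
- SAEs at 0.2-0.4 per patient-year: 0.6 to 1.3 points missed (relative 1.6-3.0%)
- fatal AEs at 0.05-0.10 per patient-year: 0.2 to 0.6 points missed (relative 2.2-3.4%)

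**6. Any AE.** At an assumed 3 per patient-year and f = 90%, the crude figure is 99.61% instead of 99.68%, a difference below 0.1 point.

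**The case against.** The strongest reply is that the SAP already recognises incomplete windows. Time at risk ends at last contact, so the main whole-trial tables carry rates that are largely free of this problem. Bleeding, the illustration above, also has Kaplan-Meier plots (SAP 7.8.1.3), and the safety-topic displays give rates for serious AEs. This stands, and it confines the point to the separate SAE, severe-AE and fatal-AE tables and the 48- and 96-week tables.

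Second, non-AE stops may carry lower risk than a common hazard implies. Worsening of the underlying disease is itself an AE, so patients who stop for it get the FU visit. AEs that began before EOT are followed to outcome (Protocol 5.2.5.2.3), so a later death from such an event can still be captured. Both arguments reduce the size; neither removes the gap for new onsets.

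Third, crude percentages already mix very different treatment durations, beside which 21 to 28 days is little. That is fair, but the shortfall here is tied to the reason for stopping and is easily avoided.

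Fourth, the AE summaries follow sponsor standards that are not in the documents, and parts of the SAP are redacted. Rates in the SAE tables may therefore be intended. The visible text does not say so.

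A reader might infer more than the documents support:
- **That the primary endpoint is biased.** Its percentage is close to saturation and its rate uses the truncated time at risk.
- **That all term-level results are unprotected.** The whole-trial SOC/PT tables carry rates.
- **That the loss could reach 0.7 to 0.8 points of the Total column, or 18-25% in relative terms.** Those values need stops at Week 12, and the points also need 80% of patients to stop then for non-AE reasons, whereas patients are asked to stay 96 weeks. The relative figure describes only the Week 12 subgroup, not a planned table.

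**Conclusion.** The mismatch is real and follows from explicit rules in both documents. Its effect is a small, one-directional under-count in the crude SAE, severe-AE and fatal-AE tables and in the 48- and 96-week AE tables. For an event of 11.1% per 52 weeks and stops at Week 96, it is 0.5 to 0.7 points within non-AE stops, about 3-4% in relative terms, and about 0.05 to 0.6 points in the Total column.

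These sizes rest on a constant hazard, EOT 0 to 7 days after the last dose, and an assumed 10-80% share of non-AE stops. The number of SAEs or deaths missed cannot be derived from the documents. No test is affected, because none is planned. This is a cheap improvement in reporting, not a flaw in the trial's main result.

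**What to change.** In SAP 7.8.1:
- State that the time at risk and exposure-adjusted rates of SAP 7.8.1.1 are added to the whole-trial SAE, severe-AE and fatal-AE tables.
- Produce those tables, and the 48- and 96-week AE tables, also with the 7-day residual effect period named in SAP 6.1, beside the 28-day versions.
- State in the SAP and the report that the 28-day window is incompletely observed for non-AE stops, and that the 7-day window is too when EOT falls on the day of the last dose.

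The cost is extra table runs and some wording. It needs no protocol amendment and no new data.

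Optional, and only if the protocol is amended for other reasons while patients are still in the trial: extend the existing 28-day telephone AE contact (flowchart footnote 9) to non-AE stops, subject to the patient's agreement after withdrawal of consent. On its own it would not justify an amendment, which would need ethics-committee and authority approval for about 160 sites in about 15 countries. For Week 96 leavers who continue nintedanib elsewhere, those 28 days are also not a drug-free residual period.

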7. STATISTICAL METHODS AND DETERMINATION OF SAMPLE SIZE

7.1 STATISTICAL DESIGN - MODEL

This is a multi-centre, multi-national, open-label clinical trial to investigate the long-term tolerability and safety of nintedanib in patients with Progressive Fibrosing Interstitial Lung Disease (PF-ILD) previously treated in a double-blind phase III placebo controlled trial (INBUILD®).

As the main objective of this extension trial is to study long-term tolerability and safety, only descriptive statistics will be used. Some limitations due to the nature of the extension trial should be considered when interpreting the data (bias in the selection of the population, no comparative arm). Further endpoints are considered as exploratory only.

This statistical paragraph deals with the analyses to be performed on the extension trial only. Although data of the parent trial will not be described in the scope of these analyses, they will be taken into account for adverse events analyses, as well as other evaluations.

7.2 NULL AND ALTERNATIVE HYPOTHESES

All analyses in this trial are descriptive and exploratory in nature. No formal statistical inferences are foreseen.

7.3 PLANNED ANALYSES

All evaluations will be based on the treated set (TS), unless otherwise stated. The TS will consist of all patients who are documented to have received and taken at least one dose of open-label trial medication.

The definition of important protocol violations (IPV) will be specified in the trial statistical analysis plan (TSAP). These IPV definitions will include consideration of important violations of entry criteria, treatment non-compliance, restricted medications and inadequate follow-up of hepatic events.

Patients will be analysed according to their randomised treatment group in the previous trial (INBUILD®) and overall.

Values collected at Visit 1 will be considered as the baseline, for this extension trial.

The main statistical analyses as described below will be performed based on all data collected during the on treatment period.

7.3.1 Primary endpoint analyses

The primary objective of the study is to assess the tolerability and safety of nintedanib, so please refer to section [7.3.4](#). Number of patients and % will be presented over the extension trial by category for adverse events overall.

7.3.2 Secondary endpoint analyses

Not applicable.

7.3.4 Safety analyses

Adverse events will be coded using the Medical Dictionary for Drug Regulatory Activities (MedDRA). Standard BI summary tables and listings will be produced. All adverse events with an onset between start of treatment and end of the REP, a period of 28 days after the last dose of trial medication, will be assigned to the on-treatment period for evaluation.

All treated patients will be included in the safety analysis. In general, safety analyses will be descriptive in nature and will be based on BI standards. No hypothesis testing is planned.

Statistical analysis and reporting of adverse events will concentrate on treatment-emergent adverse events, i.e. all adverse events occurring between start of treatment and end of the REP. Adverse events that start before first drug intake and deteriorate under treatment will also be considered as 'treatment-emergent'.

Frequency, severity, and causal relationship of adverse events will be tabulated by system organ class and preferred term after coding according to the current version of the Medical Dictionary for Drug Regulatory Activities (MedDRA) at database lock.

Laboratory data will be analysed both quantitatively as well as qualitatively. The latter will be done via comparison of laboratory data to their reference ranges. Values outside the reference range as well as values defined as clinically relevant will be summarised. Treatment groups will be compared descriptively with regard to distribution parameters as well as with regard to frequency and percentage of patients with abnormal values or clinically relevant abnormal values.

Vital signs, physical examinations, or other safety-relevant data observed at screening, baseline, during the course of the trial and at the end-of-trial evaluation will be assessed with regard to possible changes compared to findings before start of treatment.

